**Table 5.2.2-1 Possible Re-estimated Sample Sizes for Different Assumptions at First Interim Analysis**

Placebo Proportion	MEDI-563 Proportion	N (Placebo)	N (MEDI-563)	Total Sample Size	Power (%)
0.540	0.270	43	86	129	80
0.500	0.250	49	98	147	81
0.450	0.225	57	114	171	80

### 5.3 Analysis Populations

All evaluable subjects will be included in the efficacy analyses. All randomized subjects, regardless of whether they are evaluable, will be included in the safety analyses. Missing data will be treated as missing without data imputation.

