### **3.2 Enrollment and Randomization**

A subject is considered enrolled into the study once written informed consent is obtained. Once informed consent is obtained, a subject identification number (SID) will be assigned by a central system (eg, an interactive voice/web response system [IXRS]) and the screening evaluations may begin. This number will be used to identify the subject during the screening process and throughout study participation.

Enrolled subjects will be screened by investigators to assess eligibility for randomization into the study. A master log will be maintained of all enrolled subjects and will document all screening failures (ie, subjects who are consented and enrolled but not randomized), including reason for screening failure.

Subjects who fail to meet all eligibility criteria or who decline participation will not proceed to randomization.

An IXRS will be used for assignment of the SID at enrollment, randomization to a treatment arm and treatment group, and assignment of blinded investigational product kit numbers. A subject is considered entered and randomized into the study when the investigator notifies the IXRS that the subject meets eligibility criteria and the IXRS provides the assignment of a blinded investigational product kit number to the subject using the 2-step stratified randomization procedure described in Section 2.3 and displayed in Figure 2.3-1.

The procedure for study entry and randomization is as follows:

- The subject has been treated for asthma exacerbation in the urgent healthcare setting or in the EMS for  $\geq 1$  hour and meets all the inclusion and exclusion criteria.
- The investigator or designee confirms that written informed consent has been obtained and that the subject meets all eligibility criteria.
- The investigator or designee calls or logs onto the IXRS and provides the SID and subject's baseline characteristic(s) used to verify that it is the same subject, and the subject's eosinophil count.
- At the first step of randomization, the IXRS assigns a treatment arm (Treatment Arm I or II) to the subject at a 1:1 ratio. Then at the second step, IXRS assigns the subject to a treatment group at a 2:1 ratio (MEDI-563 and placebo, respectively), and assigns an investigational product kit number(s). Both steps will be done on the same call or login.
- A confirmatory fax with this information is sent to the Clinical Trial Material (CTM) Manager.

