Investigational product (MEDI-563 or placebo) must be administered as soon as possible after randomization. If there is a delay in the administration of investigational product such that it will not be administered on the day of receipt of the investigational product kit number(s), the MedImmune study monitor and/or its designee must be notified immediately.

Subjects are considered evaluable if they receive the investigational product and are followed according to the protocol through Study Day 42. Nonevaluable subjects will be replaced. Replacements, if necessary will take place after the initial randomization of all planned subjects has been completed. The replacement subject will receive the same treatment assignment as the subject being replaced.

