### **3.5 Schedule of Subject Evaluations**

All subjects who are assigned a SID and receive any investigational product will be followed according to the protocol regardless of the number of doses received, unless consent for follow-up is withdrawn. The investigator must notify the sponsor or designee of all deviations from protocol visits or evaluations and these evaluations, if applicable, must be rescheduled or performed at the nearest possible time to the original schedule. Protocol deviations will be recorded on the source document with an explanation for the deviation. The investigator must

comply with the applicable requirements related to the reporting of protocol deviations to the IRB/IEC.

Subjects will be instructed to call study personnel to report any abnormalities during the intervals between study visits and to come to the study site/bring the subject to the study site if medical evaluation is needed and the urgency of the situation permits. For emergency and other unscheduled visits to a medical facility other than the study site, medical records will be obtained by the investigator and made available to the sponsor or designee during monitoring visits.

A schedule of screening and on-study visit procedures is presented in [Table 3.5-1](#), followed by a detailed description of each visit.

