#### **4.1.2 Study Reporting Period for Adverse Events**

All adverse events that occur after a subject has received the investigational product through Study Day 84 must be reported by the investigator.

Any new sign or symptom, disease, or other untoward medical event that occurs after the subject signs the informed consent form but before the subject has received investigational product, and which may possibly be causally related to the protocol (ie, results from a

required procedure or from withdrawal of prior medication), must be reported by the investigator as an adverse event in the same way as adverse events that occur after the subject receives investigational product.

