#### **4.2.2 Study Reporting Period for Serious Adverse Events**

The reporting period for SAEs is the period immediately following the time that written informed consent is obtained through Study Day 84. After the initial SAE report the investigator is required to follow each subject proactively and provide further information on the subject's condition to MedImmune Product Safety.

All SAEs should be followed up to resolution by the investigator, even if this extends beyond the study reporting period. Resolution of an SAE is defined as the return to baseline status or stabilization of the condition with the expectation that it will remain chronic.

At any time after completion of the study, if an investigator or qualified designee becomes aware of an SAE that is suspected by the investigator or qualified designee to be related to investigational product, the event should be reported to MedImmune Product Safety.

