##### Relationship assessments that indicate an “Unlikely Relationship” to investigational product:

None:	The event is related to an etiology other than the investigational product (the alternative etiology must be documented in the study subject’s medical record).
--------------	---

*Remote:*

The event is unlikely to be related to the investigational product and likely to be related to factors other than investigational product.

Relationship assessments that indicate a “**Likely Relationship**” to investigational product:

*Possible:*

There is an association between the event and the administration of the investigational product and there is a plausible mechanism for the event to be related to investigational product; but there may also be alternative etiology, such as characteristics of the subject’s clinical status or underlying disease.

*Probable:*

There is an association between the event and the administration of investigational product, a plausible mechanism for the event to be related to the investigational product and the event could not be reasonably explained by known characteristics of the subject’s clinical status or an alternative etiology is not apparent.

*Definite:*

There is an association between the event and the administration of investigational product, a plausible mechanism for the event to be related to the investigational product and causes other than the investigational product have been ruled out and/or the event re-appeared on re-exposure to the investigational product.

For AEs that occur prior to the administration of investigational product, an assessment of protocol relatedness must be made. Protocol-related AEs may occur as a result of procedures required during the screening process (eg, blood collection, washout of an existing medication) prior to the initial administration of investigational product. For AEs that occur before administration of investigational product, only those that are assessed by the investigator as protocol-related should be reported to the sponsor. The following guidelines should be used by investigators to assess the relationship of an AE to a protocol-required procedure:

*Protocol related:*

The event occurred due to a procedure/intervention that was described in the protocol for which there is no alternative etiology present in the subject’s medical record.

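### Section 5.3 defines the safety set by randomization, while full adverse-event reporting and follow-up are tied to dosing, so any randomized but undosed subject would lower the absolute adverse-event rates

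*Protocol*

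**What the plan says.** Section 5.3 fixes the safety set: "All randomized subjects, regardless of whether they are evaluable, will be included in the safety analyses". It sets no dosing condition.

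Other sections fix when a subject enters that set and what is observed afterwards:

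- **Randomization (Section 3.2).** "A subject is considered entered and randomized into the study when the investigator notifies the IXRS that the subject meets eligibility criteria" and a kit number is assigned. This precedes the infusion. The same section provides for a gap: "If there is a delay in the administration of investigational product such that it will not be administered on the day of receipt" of the kit number, the study monitor must be told.
- **Evaluability (Section 3.2).** "Subjects are considered evaluable if they receive the investigational product and are followed according to the protocol through Study Day 42". A subject who is never dosed is therefore nonevaluable and is replaced, but remains randomized.
- **Follow-up (Section 3.5).** "All subjects who are assigned a SID and receive any investigational product will be followed according to the protocol".
- **Adverse events (Section 4.1.2).** "All adverse events that occur after a subject has received the investigational product through Study Day 84 must be reported by the investigator". For events before dosing, Section 4.4 says "only those that are assessed by the investigator as protocol-related should be reported to the sponsor".
- **Serious adverse events (Section 4.2.2).** "The reporting period for SAEs is the period immediately following the time that written informed consent is obtained through Study Day 84". This carries no dosing condition.

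Section 5.5.1 summarizes adverse events through Study Day 84, by severity and by relationship to investigational product among other factors.

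**The concern.** The denominator of a safety rate should consist of people in whom the event could have been observed under the plan. Here the denominator opens at randomization, while reporting of all adverse events opens at dosing. A subject who falls between the two counts as a subject without an event, though no post-dose observation was required.

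The protocol leaves room for such subjects. Section 3.2 anticipates delayed dosing. In the Study Day 0 list of Section 3.5, randomization is item 5 and spirometry item 8, while an FEV1 condition must be met before product is given (Section 3.1.1, criterion 14). Section 4.8 halts all further administration after certain events, which could leave a randomized subject undosed.

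Safety is the first secondary objective, and the groups are small (36 per group, 72 on MEDI-563 combined). Any dilution lowers reported rates and upper confidence limits, which is the non-conservative direction for safety.

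**Working it through.** **1. Inputs.** Planned dosed numbers are 36 per dose group, 72 combined and 36 on placebo (Section 3.4.2). The precision tables use n = 36 and n = 72 (Section 5.2.1). The number randomized but undosed is not given, so 0 to 8 is taken as an illustrative range only.

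**2. The plan's own figures.** The exact 95% upper limit for zero events is 1 − 0.025^(1/n).

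- n = 36: 1 − 0.025^(1/36) = 9.74%, printed as 9.7% in Table 5.2.1-2.
- n = 72: 1 − 0.025^(1/72) = 4.99%, printed as 5.0%.
- 3/72 = 4.2% with exact limits 0.9% and 11.7%, as printed.

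All 8 rows of Table 5.2.1-2 and all 14 rows of Table 5.2.1-1 reproduce to the printed decimal.

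**3. Dilution.** With D dosed and U undosed subjects, and no post-dose events recorded in the undosed, reported rate = true rate × D/(D + U). The relative loss is U/(D + U), the undosed share of the set.

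| Dosed | Undosed | Factor | True 10% shows as | True 20% shows as | Upper limit, 0 events |
|---|---|---|---|---|---|
| 36 | 0 | 1.000 | 10.00% | 20.00% | 9.74% |
| 36 | 1 | 0.973 | 9.73% | 19.46% | 9.49% |
| 36 | 2 | 0.947 | 9.47% | 18.95% | 9.25% |
| 36 | 4 | 0.900 | 9.00% | 18.00% | 8.81% |
| 36 | 8 | 0.818 | 8.18% | 16.36% | 8.04% |
| 72 | 0 | 1.000 | 10.00% | 20.00% | 4.99% |
| 72 | 1 | 0.986 | 9.86% | 19.73% | 4.93% |
| 72 | 2 | 0.973 | 9.73% | 19.46% | 4.86% |
| 72 | 4 | 0.947 | 9.47% | 18.95% | 4.74% |
| 72 | 8 | 0.900 | 9.00% | 18.00% | 4.51% |

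Worked case: 10 events in 36 dosed subjects is 27.8%. With 2 undosed added it is 10/38 = 26.3%, a relative loss of 2/38 = 5.3%.

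**4. Comparison between groups.** If the undosed share is the same in both arms, both rates carry the same factor f. The ratio is unchanged, and the absolute difference shrinks by f. If the shares differ, the ratio moves too: with a true rate of 10% in both arms, 2 undosed per 36 dosed in one arm and none in the other gives 9.47% against 10.00%.

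**5. With the set tied to dosing.** U = 0 by definition, the factor is 1, and the denominators are the dosed numbers.

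**The case against.** The strongest reply is that the undosed group may be empty. There is one infusion. Randomization is done on Study Day 0 after eligibility has been verified, Section 3.2 requires dosing as soon as possible afterwards, and a delay past that day must be notified at once. The replacement rule also covers dosed subjects lost before Day 42, so it does not show that undosed subjects are expected in any number. All of this stands and limits the size of the point. It does not make the definition right.

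Several stronger readings are tempting, and the documents do not support them:

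- *That no adverse events are collected in undosed subjects.* Serious events are reportable from consent (Section 4.2.2) and protocol-related events before dosing are reportable (Sections 4.1.2 and 4.4). What is missing is a requirement to report all events after the point at which dosing would have occurred.
- *That undosed subjects are dropped from follow-up.* Section 3.5 commits to following those who receive product. It does not say that only they are followed.
- *That the rule tabulates subjects as randomized, so a kit error would be shown under the wrong treatment.* Section 5.3 says who is in the set, not how they are grouped. Grouping may properly be left to the statistical analysis plan.
- *That an undosed subject and the replacement are counted twice.* They are two people; the only effect is the dilution already shown.
- *That the precision tables are wrong.* They are planning illustrations at fixed n, and they reproduce.

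**Conclusion.** The point holds as a mismatch between a stated denominator and stated data collection. Section 5.3 is an explicit rule: an analysis plan that follows it inherits the mismatch, and one that limits safety to dosed subjects departs from the protocol.

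The effect is on absolute rates and upper limits, always downward, by the undosed share: about 3% relative for 1 undosed per 36 dosed, 5% for 2 and 10% for 4. These figures assume that undosed subjects contribute no post-dose events. The true count is not in the documents, may be zero and is probably small.

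A reader might infer that the comparison of MEDI-563 with placebo is biased. That would need the undosed share to differ by arm, and in a double-blind trial the documents give no reason to expect it. Confidence is high on the wording and low on any material effect. It should be corrected because the correction costs almost nothing, not because a safety conclusion has been shown to depend on it.

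**What to change.** Replace the safety sentence in Section 5.3 with: *All subjects who receive any amount of investigational product will be included in the safety analyses, by treatment actually received.* Add that serious adverse events from consent and protocol-related pre-dose events in randomized but undosed subjects are listed separately, so no collected safety information is lost.

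The cost is one or two sentences in Section 5.3 and the same definition in the statistical analysis plan. Data collection, sample size, power and the efficacy population do not change.

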### 5.4 Primary Endpoint

The primary objective of this study is to evaluate the effect of two IV dose regimens of MEDI-563 (0.3 and 1.0 mg/kg) on the proportion of subjects with asthma exacerbations (relapsed or de novo) at Week 12 in adult subjects who required an urgent healthcare visit for treatment of an acute asthma exacerbation. The formula that will be used to evaluate the proportion of subjects with asthma exacerbations in the combined MEDI-563 treatment groups at Week 12 will be as follows:

- $$\frac{\text{(Number of subjects with at least one asthma exacerbation in the combined MEDI-563 treatment groups [0.3 and 1.0 mg/kg] at Week 12)}}{\text{(Number of total evaluable subjects in the combined MEDI-563 treatment groups [0.3 and 1.0 mg/kg] at Week 12)}}$$

The Fisher’s exact test will be performed for testing the differences in proportion of subjects with asthma exacerbations at Week 12 between the combined MEDI-563 treatment groups and the placebo group at an alpha level of 0.05.

The number of asthma exacerbations at Week 12 for each MEDI-563 treatment group (0.3 and 1.0 mg/kg) versus placebo will also be reported. The Fisher’s exact test may be performed for testing this endpoint.

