██████████; Final  
dying suddenly (within 2 hours on onset of symptoms) while an eosinophilic infiltrate is more common in those dying from more protracted asthma crises. Many lines of evidence implicate eosinophils as one of the main causative cells of asthmatic airway inflammation (James et al, 2005). Peripheral blood eosinophilia is a risk factor for relapse of acute asthma (Janson and Herala, 1992). In subjects with peripheral blood eosinophilia, the risk of dying from asthma was 7.4 (confidence interval, 2.8-19.7) times greater than in those without eosinophilia (Ulrik and Frederiksen, 1995). Moreover, reductions in sputum eosinophilia with corticosteroids lead to better asthma control than the use of clinical guidelines (Green et al, 2006). Thus, controlling eosinophilia is associated with better asthma outcomes.

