## 2.3 Overview

### Study Design

This is a Phase 2, randomized, double-blind, placebo-controlled study to evaluate the effect of two IV dose regimens of MEDI-563 (0.3 and 1.0 mg/kg) on the proportion of asthma exacerbations (relapse and de novo) at Week 12 in adult subjects who required an urgent healthcare visit for treatment of an acute asthma exacerbation. Approximately 15 to 20 sites in North America will participate in this study. At least 108 evaluable subjects will be randomized using a 2-step stratified randomization procedure. The first step (Step 1) will randomize subjects in a 1:1 ratio to Treatment Arms I or II, and the second step (Step 2) will randomize subjects in each treatment group in a 2:1 ratio to receive a single IV dose of MEDI 563 or placebo as described in [Figure 2.3-1](#). Prior to being randomized into a treatment arm subjects will be stratified by baseline eosinophil levels in peripheral blood ( $>450$  eosinophils/mm^3 vs.  $\leq 450$  eosinophils/mm^3). However, no subjects will be excluded based on screening eosinophil levels in peripheral blood.

Subjects are considered evaluable if they receive the investigational product, and are followed according to the protocol through Study Day 42. Nonevaluable subjects will be replaced and the new subject will receive the same treatment assignment as the replaced subject.

Investigational product (MEDI-563 or placebo) will be administered on Study Day 0 (within 7 days of meeting eligibility criteria). The subject's FEV1 must be  $\geq 30\%$  predicted prior to administration of the investigational product.

Investigational product will be administered as a single IV infusion over a period of at least 30 minutes through a 0.22 µm protein-sparing/low in-line filter, which will be supplied by the sponsor. If the subject weighs  $\geq 130$  kg, the infusion time will be increased to at least 60 minutes. Subjects will be followed for a total of 24 weeks after administration of the investigational product.

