### 3.4.2 Treatment Regimen

At least 108 evaluable subjects will be treated in this study, with 72 subjects receiving a single IV dose of MEDI-563 (0.3 or 1.0 mg/kg) and 36 subjects receiving a single IV dose of placebo as described in [Table 3.4.2-1](#). Investigational product (MEDI-563 or placebo) will be administered on Study Day 0 (within 7 days of meeting eligibility criteria) once the subject has demonstrated an FEV1 of  $\geq 30\%$  predicted.

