## **5 Statistical Considerations**

### **5.1 General Considerations**

All data will be provided in data listings sorted by treatment groups (MEDI-563 0.3 mg/kg, MEDI-563 1.0 mg/kg, or placebo), and visit number. Summary data will be presented in tabular format by treatment groups. Categorical data will be summarized by the number and percentage of subjects in each category. Continuous variables will be summarized by descriptive statistics including N, mean, standard deviation, median, and range. Statistical hypothesis testing, if appropriate, will be performed for the primary endpoint with a 2-sided test.

A comprehensive statistical analysis plan will be developed and approved prior to the database lock.

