### **5.2 Sample Size and Power Calculations**

#### **5.2.1 Planned Sample Size**

Sample size calculations have been performed for the primary endpoint of proportion of subjects with asthma exacerbations at Week 12 to allow for hypothesis testing. Sample size calculations are based on Fisher's exact test with  $\alpha = 0.05$  (2-sided) for testing the difference between the combined MED-563 treatment groups ( $n=72$ , 0.3 mg/kg and 1.0 mg/kg) and the combined placebo group ( $n=36$ ). Assumptions include: (1) The proportion of placebo subjects with asthma exacerbations at Week 12 is 60% and (2) There will be  $\geq 50\%$

reduction in the proportion of subjects with asthma exacerbations at Week 12 in the combined MEDI-563 (0.3 and 1.0 mg/kg) treatment groups. The sample size may be re-estimated using the proportion of subjects with asthma exacerbations (relapsed or de novo) up to the first interim analysis to preserve the power around 80% if the proportion of subjects with asthma exacerbations is different from the assumptions listed above.

There will be no adjustment on Type 1 error rate for sample size re-estimation in this study. However, the true overall type I error rate will be greater than 0.05 if the multiplicity adjustment is taken into account in the calculation. With 108 evaluable subjects, the statistical power to detect statistically significant differences in the proportion of subjects with asthma exacerbations at Week 12 in the combined MEDI-563 treatment groups and the placebo group will be 80% based on the above assumptions. Power calculations were performed using nQuery Advisor software program Version 6.01.

Table 5.2.1-1 and [Table 5.2.1-2](#) present the probability of observing at least one infrequently occurring event when assuming a range of potential observed event rates and exact binomial 95% confidence intervals to assess the precision of estimates of the event rate for each individual treatment group (n=36) and combined MEDI-563 treatment group (n=72).

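### The primary test is a pooled Fisher's exact test that ignores the eosinophil strata used at randomization; it is valid and delivers the planned power, but gives up about 4 points that an uncorrected stratified test would recover

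*Protocol*

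**What the plan says.** The Study Abstract and Section 2.3 state: "Prior to being randomized into a treatment arm subjects will be stratified by baseline eosinophil levels in peripheral blood", with a cut at 450 cells/mm3. Section 3.2 has the site give the eosinophil count to the randomization system. Section 1.1 says: "Peripheral blood eosinophilia is a risk factor for relapse of acute asthma". Relapse is part of the primary endpoint.

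Section 5.4 and the Assessment of Endpoints part of the Study Abstract then name a Fisher's "exact test will be performed for testing the differences in proportion of subjects with asthma exacerbations at Week 12". It compares the two pooled active doses with placebo, at alpha 0.05. Section 5.1 says that hypothesis testing "will be performed for the primary endpoint with a 2-sided test". The stratum is not mentioned. Sections 5.5.2 and 5.5.3 offer Fisher's test for Weeks 4 and 24.

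Section 5.2.1 sizes the trial on the same Fisher's test and states 80% power with 108 evaluable subjects.

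**The concern.** Two features of the stated analysis pull the same way. Fisher's exact test conditions on both margins, so with 108 subjects it rejects less often than its nominal 5%. And when allocation is balanced within a prognostic stratum, a pooled test overstates the variance of the treatment difference and becomes more conservative still. The stratum is collected before randomization and has to be supplied in order to randomize, so a test that uses it needs no additional data. At stake is efficiency in a small trial whose sample size may rise to as many as 171 under Table 5.2.2-1.

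**Working it through.** **Inputs from the protocol.** Section 3.4.2: "with 72 subjects receiving a single IV dose of MEDI-563 (0.3 or 1.0 mg/kg) and 36 subjects receiving a single IV dose of placebo". Section 5.2.1: "The proportion of placebo subjects with asthma exacerbations at Week 12 is 60" percent, with at least a 50% "reduction in the proportion of subjects with asthma exacerbations at Week 12 in the combined MEDI-563 (0.3 and 1.0 mg/kg) treatment groups", so 60% versus 30%. Two-sided alpha is 0.05.

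**Inputs that are assumed.** The protocol gives neither the share of subjects above 450/mm3 nor the effect of the stratum on the Week 12 proportion. The main table takes 40% in the high stratum (0.4 × 36 = 14.4, so 14 placebo; 0.4 × 72 = 28.8, so 29 MEDI-563) and a 50% reduction in each stratum.

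**Step 1: reproduce the stated power.** With b the binomial probability and p_F the two-sided Fisher p-value,

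power = Σx Σy b(x; 36, 0.60) · b(y; 72, 0.30) · 1{p_F(x, y) ≤ 0.05} = 81.1%.

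The stated 80% reproduces.

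**Step 2: actual size of Fisher's test.** The same sum with one common proportion p gives 3.2% at p = 0.1, 3.8% at 0.3, 0.4 and 0.6, and at most 4.0% for any p. At the re-estimated sizes 43/86, 49/98 and 57/114 the maximum is 4.0%, 4.2% and 4.4%.

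**Step 3: power against alternatives.** The CMH statistic without continuity correction, over strata h with n_h placebo subjects, m_h active subjects, N_h = n_h + m_h, x_h placebo events and t_h total events, is

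|Σ(x_h − t_h n_h/N_h)| / √Σ[n_h m_h t_h (N_h − t_h) / (N_h²(N_h − 1))], compared with 1.96.

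Simulated power (300,000 trials per setting):

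| Placebo rate, high / low stratum | Fisher | Pearson chi-square, unstratified | CMH, uncorrected | CMH, continuity-corrected |
|---|---|---|---|---|
| 60% / 60% (not prognostic) | 81.1% | 85.5% | 85.3% | 80.7% |
| 75% / 50% | 80.8% | 85.4% | 86.7% | 81.4% |
| 85% / 43% | 80.9% | 85.7% | 88.8% | 83.6% |

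The assumed rates average to the protocol's 60%: 0.4 × 75 + 0.6 × 50 = 60.0, and 0.4 × 85 + 0.6 × 43 = 59.8.

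**Step 4: split the gain.** Uncorrected CMH minus Fisher is 85.3 − 81.1 = 4.2, 86.7 − 80.8 = 5.9 and 88.8 − 80.9 = 7.9 points. Leaving Fisher for the unstratified chi-square already gives 4.4, 4.6 and 4.8 points. Stratifying therefore adds nothing in the first setting, 86.7 − 85.4 = 1.3 in the second and 88.8 − 85.7 = 3.1 in the third.

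**Step 5: vary the assumptions.** With the high stratum at 25% to 50% of subjects and a stratum odds ratio of 1 to 5, the gain of uncorrected CMH over Fisher runs from 4.2 to 7.4 points. The 85%/43% setting corresponds to an odds ratio of (0.85/0.15)/(0.43/0.57) ≈ 7.5.

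**Step 6: size when the stratum is prognostic.** With stratum rates of 60% and 20% in both arms (odds ratio 1.5/0.25 = 6), Fisher's size falls to about 2.3%. Uncorrected CMH stays at 4.8% to 5.0%.

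**Step 7: in subjects.** At 60% versus 30%, Fisher's power is 84.4% with 114 subjects and 85.9% with 117. Matching the 85.3% of uncorrected CMH at 108 would take 117, or 9 more subjects.

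**The case against.** The strongest reply is that nothing here is in error. The trial was sized with Fisher's test, the same test is primary, and the exact power of 81.1% meets the stated 80%. A positive result would be valid. This stands: a reader might infer that the trial is underpowered, that its power is misstated or that its p-value is unreliable in the liberal direction, and the protocol supports none of these.

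A reader might also infer that the whole loss comes from ignoring the stratum. Step 4 shows otherwise: about 4.5 points come from Fisher's conservatism and about 0 to 3 from stratifying. The upper figures need a strong stratum effect, for which the protocol offers one qualitative sentence.

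Fisher's slack also has a use. Section 5.2.1 makes no type I error adjustment for sample size re-estimation and acknowledges that the overall error exceeds 0.05 once multiplicity is counted. Under one assumed reading of the rule (15 placebo subjects at the interim, and a placebo rate of 45% to 55% triggering the tabulated sizes), Fisher's size is at most 4.2% over null rates of 30% to 60%, against up to 5.2% for the unstratified chi-square. That is a real, small cost of changing the test.

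Leaving the matter to the statistical analysis plan does not answer the point. That plan could add stratified supportive analyses, but the protocol already names the primary test.

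**Conclusion.** The point holds as a cheap improvement, not as a correction of an error. The stated analysis does not use the randomization strata, and the test chosen runs at 3.2% to 4.0% instead of 5%. The loss of about 4 points against uncorrected CMH follows from the protocol's own sample sizes, event rates and alpha, and needs no assumption about eosinophils. A loss of 7 to 8 points, and a size near 2.3%, hold only with stratum odds ratios of about 5 or more, which the protocol neither states nor excludes.

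**What to change.** In Section 5.4 and the matching part of the Study Abstract, make the primary test a Cochran-Mantel-Haenszel test **without continuity correction**, stratified by the eosinophil stratum recorded at randomization. Report the Mantel-Haenszel risk difference with its 95% confidence interval. Keep Fisher's exact test as a sensitivity analysis, and use the same stratified test at Weeks 4 and 24.

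The variant has to be named. The continuity-corrected CMH reaches only 80.7%, 81.4% and 83.6% in the three settings above. An exact conditional CMH gains only 0 to 1 point over Fisher at stratum odds ratios of 2 or less, and 4 to 5 points at an odds ratio of 5. Either would serve as a check, but as the primary test it would recover little when the stratum is weakly prognostic.

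The change is one of wording, made before the first interim analysis is unblinded, with no new data or visits. Its costs are an asymptotic p-value (simulated size 4.8% to 5.0%) and the loss of the slack that partly offsets the unadjusted re-estimation; the amended text should acknowledge the second.
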